To fill this gap, we have developed a first-of-its-kind school-based intervention for SGM youth, Proud & Empowered! (P&E). The multi-level program was developed over the last 9 years through (a) psychometric, developmental, and acceptability studies funded by the NIH, foundations (Zumberge), and intramural sources; (b) a collaboration with three SGM youth dropin centers, more than 100 SGM youth, and a dozen academic and clinical experts; and (c) an exploratory study (R21MD013971) to assess the feasibility and preliminary efficacy of the intervention. Given encouraging findings, we now propose to employ a large-scale randomized controlled trial (RCT) with 24 schools in Los Angeles to establish program efficacy. At intervention sites (n = 12), after the 10-session small group portion of the intervention with SGM youth is completed, peer allies (who are identified through a popular opinion leader model) are invited to participate in 4-session leadership program focused on changing SGM-related school climate. This is followed by student-led implementation of environmental change strategies at the school level focused on key domains of school climate described by Thapa et al. (2013): safety, relationships, teaching and learning, and institutional environment. At the SGM student

level, analysis will focus on the hypothesized mechanism of change (minority stress) and key behavioral health outcomes (depression, anxiety, PTSD, suicidality, substance use).

Change in school climate will also be assessed qualitatively using content analysis and observational methods in the intervention and post-intervention years. Our specific aims are to:
1) Determine participant-level efficacy of the intervention in an RCT with 24 schools, 2)
Determine the schoolwide intervention effects on (a) reporting of minority stress and behavioral health outcomes among all SGM students and (b) perceptions of school climate (norms, attitudes, beliefs, bullying behaviors toward SGM youth, policies) among all students, and 3)
Examine factors that may affect intervention success (e.g., fidelity of implementation, barriers or facilitators to implementation, school or student characteristics) to prepare the intervention for future dissemination.

Participants

1. Inclusion Criteria:

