LGBTQ Cohort: Recruitment flyers (Recruitment Flyer for P&E.docx) will be distributed by school counselors to students in participating schools. Flyers will not be posted in any non-public area, rather they will be handed out to school clubs (i.e. Gay/Straight Alliance, Rainbow Club, etc) and to students directly by student counselors. Flyer contains information about the study and contact information for student counselors in their school. Students who endorse interest will have private and confidential meetings with their counselor regarding participating in this study. In week four of the school year, we will randomly select 12 names at each school from the LGBTQ+ youth identified via these recruitment methods to be invited to participate in the LGBTQ+ youth cohort portion of the study. These youth will be invited to a first P&E session, where they will be provided the link to the Proud & Empowered e-consent (or consent if they are 18+) form (P&E Assent Consent WUSTL 9.22.22.rtf), also hosted on RedCap and accessible via phone or school assigned tablet/computer.

Make Space Allies: To identify POL allies, P&E facilitator ([name]) will introduce the Make Space program, student advocacy and discuss the meaning of LGBTQ+ allies with our P&E students during session 4: Peers and Relationships. Students will then discuss allies whom they feel would benefit the Make Space project. Students will then begin nominating individuals who can serve as a popular opinion leader (POL) for the Make Space project. Students will select potential POL allies in session 6. School counselors/liaisons will then meet with these identified students and assess for the student's willingness to operate as an effective LGBTQ ally (e.g., willingness to provide visible support for SGM students), and students who are not interested, for any reason (related to topic or otherwise), will not be asked to participate. After screening each POL for interest in participation, Study Coordinator will then randomly select ten of the students identified to participate in the Make Space intervention portion of the study. Students who report interest and are chosen for participation will provide e-assent (or consent if they are 18+), similar to the process described for LGBTQ+ youth (on RedCap using phones or tablets). See "Make Space Intervention Procedures" below for more information on the Make Space assent/consent process.

Waiver of Parental Consent

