Proud & Empowered! Intervention: The proposed study is intended to rigorously test the efficacy of Proud & Empowered! (P&E) program in a large-scale RCT with 24 high schools across the Greater Los Angeles Area. Schools will be randomly assigned to an intervention or control condition. Schools assigned to the intervention condition will be further randomized to receive either just the P&E direct intervention or both P&E and Make Space. Detailed information on each program (Proud & Empowered! and Make Space) can be found in sections below. LGBTQ participants in the intervention schools will participate in P&E, whereas those attending control schools will complete only study survey measures during the study on the same timeline (all three time points) as the intervention schools.

LGBTQ Youth Procedures: For LGBTQ P&E participants, measures (information on measures can be found in the *Instrumentation* section below) will be obtained at three time points: the beginning of the P&E intervention (September), after the intervention period (November), and at the conclusion of the school year (May). LGBTQ+ student participant survey can be found in the attachments section as "Y2 P&E Survey.docx". LGBTQ+ youth participants will create a Unique ID, which the study team will use to link measures taken over time. Detailed information on recruitment of LGBTQ youth participants can be found in the *Recruitment* section above. School counselor will ensure there is a time and space available for each student to meet for a 45-minute intervention session once per week for 10 weeks. The study activities will occur at the school during school hours and the school counselor will ensure students can discreetly participate in the intervention sessions by either 1) grouping participating youth into the same homeroom/advisory period where the intervention will administered by Study Facilitator/Study Coordinator, or 2) providing students with a counseling slip, allowing them to miss a class to

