participate in the intervention session. Schools will choose what works best for them. If option 2 is selected, intervention sessions will be staggered and run during a different class period each week so that participating youth do not miss the same class every week. Study staff ([name]) will present adolescents with information sheets/assent, or informed consent from those aged 18 or older, and obtain assent/consent in order to keep as little identifying information about LGBTQ+ participants as possible. Next, each LGBTQ participant will create a unique identification code that will be used in the participant's survey entries to link successive data points. Surveys will be self-administered on tablets, laptops, or cell phones. The data manager and study facilitator at the study site will track participant names and unique identifiers to keep track of the number of sessions attended by students (dosage). School staff will not have access to participant data from surveys. Youth who turn 18 during the study will complete an informed consent.

10-week P&E Intervention Procedures: A PDF of the Proud & Empowered intervention program can be found in the attachments section of this IRB application as "Proud & Empowered.pdf". The 10-week protocol includes an introductory and data collection session, then sessions on Stress and Coping, Disclosure, Families, Peers and Friendship, School-related Stress, Spirituality/Religion, Social Justice, Health and Wellness, and a final Celebration and data collection session. Each session runs about 45 minutes and will be Facilitated by MSW-level study staff. We have formalized the process for tracking fidelity and other outcomes after each session via a post-session facilitator feedback form. This form (uploaded to "attachments" section as "Post-Session Data Collection.docx) will be completed by the intervention facilitator ([name]) immediately after each session. Data to collect includes attendance (dosage), intervention location, and information on participant engagement and collaboration.

School Policy Scan

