Data Analysis

A series of analyses will be conducted to thoroughly investigate the program effects and its fidelity on outcomes of interest. First, a cluster-randomized repeated measures ANOVA will be used to examine the intervention effects on minority stress, behavioral health outcomes, and coping skills among the cohort of SGM adolescents who participate in the small group intervention and their control-school counterparts. Second, qualitative content and observational analysis by study staff will be used to conduct a baseline policy scan in the intervention year, inform Make Space participant activities, and evaluate change in policies over the course of the year.

Data Protection

All survey data will be coded using a unique code selected by each participant. Coded data will be held separately from all identifying data, such as recruitment information. Assent/consent will be collected in a separate survey though RedCap in order to keep as little identifying information about LGBTQ+ participants and POL participants as possible. All contact information used for recruitment be destroyed at the conclusion of the study. Downloaded data will be stored on dual-authentication and password-protected computers. Only the PI and authorized study staff will have access to survey data.

Dissemination of Findings

The proposed study plans to consistently disseminate findings from study data and – if warranted – to provide broad access to the final intervention program. The dissemination plan aims to inform research on minority health, risk and protective factors among SGM youth. Research findings will also be disseminated through peer-reviewed journals, national conferences, and relevant compendiums of intervention research if possible (e.g., Cochrane).

Data Safety Monitoring Board (DSMB)

The DSMB will meet quarterly during the first year of the project and annually thereafter and is composed of recognized experts in SGM clinical ([name]) and adolescent research ([name]; [name]) with no direct involvement in the study. The DSMB will be charged with ensuring the highest standards for participant safety and data

quality. Initially, the board will review the study design, instruments and methods, recruitment criteria, intervention plan, and data analytic plan. It will provide recommendations to safely achieve our goals. Subsequent meetings will focus on monitoring study participant enrollment, safety, and protocol adherence (*see DSMB and Letters of Support*).

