POL Allies: To identify POL allies, we adapt methods used successfully in school-based anti-smoking campaigns. That is, the school wide surveys will also ask students to list the names of five students in their school who they “respect,” “look up to” and “consider good leaders”. The top twenty nominated students (POLs) will be contacted by Study Coordinator and screened for interest in participating in the school climate portion of the program. Other than the biostatistician, PI and Study Coordinator, no one will know the identity of these twenty individuals. This screening will assess for the student’s willingness to operate as an effective LGBTQ ally (e.g., willingness to provide visible support for SGM students), and students who are not interested, for any reason (related to topic or otherwise), will not be asked to participate. After screening each POL for interest in participation, Study Coordinator will then randomly select ten of the students identified to participate in the school-wide intervention portion of the study.

Methods

Proud & Empowered! Intervention: The proposed study is intended to rigorously test the efficacy of Proud & Empowered! (P&E) program in a large-scale RCT with 24 high schools across the Greater Los Angeles Area. Schools will be randomly assigned to an intervention or control condition. LGBTQ participants in the intervention schools will participate in P&E, whereas those attending control schools will complete only study survey measures during the study on the same timeline (all three time points) as the intervention schools.

LGBTQ Youth Procedures: For LGBTQ P&E participants, **measures (information on measures can be found in the *Instrumentation* section below) will be obtained at three time points: the beginning of the P&E intervention (September), after the intervention period (November), and at the conclusion of the school year (May).** LGBTQ+ youth participants will create a Unique ID that study team will use to link measures taken over time. Detailed information on

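### The cohort's repeated measures ANOVA is not stated to adjust for September; a baseline-adjusted, school-level analysis of the continuous scales would be more precise, at a small but real cost

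*Protocol*

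**What the plan says.** The cohort analysis is one sentence, the same under Data Analysis in the Protocol and in the Combined protocol and SAP: "a cluster-randomized repeated measures ANOVA will be used to examine the intervention effects on minority stress, behavioral health outcomes, and coping skills". It names no covariate, treatment contrast, error term or degrees of freedom. The multilevel regression in the Combined document's Data Analysis is for school-wide outcomes, not for this cohort.

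The unit of randomisation is the school: "Schools will be randomly assigned to an intervention or control condition" (Combined document, Methods). Objectives gives 24 schools, 12 of them intervention sites, and Recruitment selects 12 youth per school. LGBTQ Youth Procedures places surveys in September, November and May, with control schools on the same timeline, so a September value is planned in both arms.

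On enrolment, the Protocol's Recruitment section says of the selected youth: "These youth will be invited to a first P&E session, where they will be provided the link to the Proud & Empowered e-consent". The 10-week P&E Intervention Procedures put the first survey in that session ("The 10-week protocol includes an introductory and data collection session"). Neither document says when schools are randomised relative to youth recruitment.

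**The concern.** With 24 randomised schools precision is scarce, and the September measurement is already planned. When September is one of the repeated responses, the treatment effect is normally read from group-by-time, which is change from September. Change subtracts the whole September value, and with it the September noise. Adjustment subtracts only the part that predicts follow-up, so its variance is lower unless the wave correlation is very high. At stake is power that could be had without collecting more data. The follow-up average is used below as a convenient single contrast; the documents name none.

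**Working it through.** **Nothing to reproduce.** The documents give no power calculation, effect size, SD, ICC or wave correlation.

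**Inputs from the documents.** 12 v 12 schools, m = 12 youth per school, three waves.

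**Assumptions.** Two-sided 5%, SD 1, ICC 0.05, effect 0.3 SD at November and May, no loss, the same correlation r between any two waves at student and school level, intervention schools pooled.

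**Variance at one wave.** School mean: V = ICC + (1 − ICC)/m = 0.05 + 0.95/12 = 0.1292. Difference between arms: b = 2V/12 = 0.02153.

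**Follow-up average, (November + May)/2.**
- Change from September: variance 1.5(1 − r)b, tested on t(22). At r = 0.6: 0.6 × 0.02153 = 0.01292, SE 0.1137, 0.3/0.1137 = 2.64.
- Adjusted for the September school mean: 0.5(1 − r)(1 + 2r)b, times 1 + 1/20 = 1.05 for estimating the slope from 24 schools, tested on t(21). At r = 0.6: 0.44 × 0.02153 × 1.05 = 0.00995, SE 0.0997, 0.3/0.0997 = 3.01.
- Variance ratio, adjusted to change: 1.05(1 + 2r)/3. It reaches 1 at r = (3/1.05 − 1)/2 = 0.93.

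**Two-df test.** The ANOVA group-by-time test has noncentrality Σ(d − mean d)²/[(1 − r)b] on F(2,44). For effects (0, 0.3, 0.3) the sum is 0.04 + 0.01 + 0.01 = 0.06; at r = 0.6 this gives 0.06/0.00861 = 6.97. The adjusted counterpart combines the adjusted average with the May-minus-November contrast, on F(2,21.5), and was simulated on school means.

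| r | variance ratio | average: change | average: adjusted | 2-df: ANOVA | 2-df: adjusted |
|---|---|---|---|---|---|
| 0.5 | 0.70 | 62% | 77% | 52% | 66% |
| 0.6 | 0.77 | 71% | 82% | 62% | 71% |
| 0.7 | 0.84 | 83% | 89% | 75% | 80% |
| 0.8 | 0.91 | 95% | 96% | 91% | 92% |

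Simulation of school means agrees with the closed form. With no effect and no September difference at r = 0.6, both adjusted tests reject in about 5% of runs.

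**Sensitivity.**
- ICC, at r = 0.6: the 2-df pair is 78 v 85% at ICC 0.01 and 49 v 57% at ICC 0.10.
- School-level r of 0.9 with student-level r of 0.6: 2-df 78 v 82%, average 85 v 90%.
- Effect in November only: effects (0, 0.3, 0) give the same sum of squares, 0.06, so the ANOVA stays at 62% at r = 0.6. The adjusted joint test has about 63%. At r = 0.8 both have about 91%. The adjusted average has only about 30% at r = 0.6.

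**Stable September difference, no treatment effect.** If the arms differ by δ at all three waves, change from September removes it. Adjustment has slope r and leaves (1 − r)δ: at r = 0.6 and δ = 0.1 SD, 0.4 × 0.1 = 0.04 SD. Simulated type I error of the adjusted average is about 6.5% at δ = 0.1 SD, 11.5% at 0.2 and 19% at 0.3. The change and group-by-time tests stay at about 5% throughout.

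**The case against.** The strongest objection is that the choice trades precision against bias. If youth decide to enrol knowing their school's allocation, the arms may differ in September for reasons other than chance. Consent at a first P&E session makes that plausible. Change from September then holds its error rate when the difference is stable, and adjustment does not. This stands, and it is why the change analysis should be kept. It does not make change the safer choice in every case: if the September difference partly reflects regression to the mean, adjustment may do better.

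Second, the gain depends on the contrast, on r and on a lasting effect. On the 2-df test it is about one point at r = 0.8 and close to nil for a November-only effect. This also stands; the direction for the follow-up average is robust up to r of about 0.93, but the size is not.

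Third, the usual form of the ANOVA is an inference, because the sentence fixes no contrast. A reader might infer that the trial will test a group main effect over all three waves. That would dilute 0.3 SD to 0.2 SD and have about 33% power at r = 0.6. No section says this test will be used, so the figure cannot be held against the plan. A reader might also infer that students will be analysed as independent. The ANOVA is called cluster-randomized in both documents, so some allowance for schools is intended, although the error term is not given.

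Fourth, a linear model need not suit suicidality or substance use. This is right, and the recommendation is limited accordingly.

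**Conclusion.** The point holds as an efficiency improvement with a stated trade-off. The documents do not say that September is a covariate. For the continuous scales, adjustment at school level cuts the variance of the follow-up average by about 30%, 23%, 16% and 9% at r = 0.5, 0.6, 0.7 and 0.8 relative to change, with the slope cost included. These sizes rest on the assumed exchangeable correlation; the power figures rest also on the assumed ICC, effect and full retention.

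Two stronger conclusions are tempting and not supported. One is that the planned ANOVA is invalid or wastes September altogether: a group-by-time test at school level uses September, holds its error rate, and at high r is nearly as powerful. The other is that adjustment is virtually free: the residual bias under enrolment after allocation is known is a real cost, and the documents do not rule that situation out. How the two intervention regimens enter the test, which contrast is primary, and how missing follow-up is handled are separate gaps in specification and are not part of this point.

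**What to change.** For the continuous scales, state in the SAP:

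- **Main analysis.** A linear mixed model of November and May with arm, wave, arm-by-wave and the September value of the same measure (youth level and school mean), and with random effects for school, school-by-wave and student. Use degrees of freedom based on the 24 schools, about 21–22 per contrast.
- **Keep the school-by-wave term.** Without it, type I error of the arm-by-wave test in this replacement model is about 11.5% at ICC 0.05 and r = 0.6, and about 6.7% if the school-level correlation is 0.9. This is a caution about the new model, not a finding about the plan.
- **Fallback.** The equivalent analysis of the 24 school means if a variance is estimated at zero, which occurred in 38% of simulated fits at ICC 0.05.
- **Sensitivity analysis.** Change from September (group-by-time), also tested at school level, with September means reported by arm. State when schools are randomised relative to youth recruitment.
- **Binary or count outcomes**, such as suicidality and substance use: a suitable generalized model with the same September adjustment.

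The cost is SAP wording and standard software, with no new data. Statistically it is one degree of freedom and about 5% of variance for the school-mean slope, about 21 rather than 44 denominator degrees of freedom for the joint test, and a rule for missing September values. The change should be made before outcomes are seen by arm.

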All measures are valid and reliable psychometric tests. As this is a quantitative study, all measures are closed-ended and survey-based. Information on each specific measure is as follows:

Sexual Minority Adolescent Stress Inventory: 54-item survey across 10 domains of minority stress. Assesses experiences of minority stress among adolescents. Each statement reflects past-30-day thoughts, feelings, and situations a person may have experienced.

Beck Anxiety Inventory: 21-item self-report assessment of anxiety symptoms.

PTSD Checklist for DSM-5 (PCL-5): 20-item self-report assessment of post-traumatic stress disorder (PTSD) symptoms which addresses all 20 DSM-5 symptoms of PTSD.

Beck Depression Inventory: 21-item self-report assessment of depression symptoms and severity of depression.

Adapted CSSRS Suicide Questions (Columbia Suicide Severity Rating Scale): Six items assessing current suicidality that were adapted from the longer, treatment-based Columbia Suicide Severity Rating Scale

Youth Risk Behavior Survey Substance Use Questions: Measures individual's usage of various substances in their lifetime and within the past 30 days as well as the ways in which individuals have used marijuana, tobacco, or nicotine in the past 30 days.

Coping Strategies Inventory: 16-item assessment measuring specific coping strategies people use in response to stressful events with each item assessing components of Problem Solving, Cognitive Restructuring, Social Support, Expressed Emotions, Problem Avoidance, Wishful Thinking, and Social Withdrawal.

LGBTQ+ Coping: 20-item assessment measuring ways individuals cope with stressors that are specifically related to being LGBTQ+ over the past 3 months.

California Healthy Kids Survey General Bullying and Gender Identity/Sexual Orientation-Based Harassment Module: Assesses students' perceptions of harassment experiences on school campus among the general student population in addition to bullying and harassment experiences on school campus specific of students who identify as, or are perceived to be, lesbian, gay, bisexual, transgender, questioning, or gender nonconforming.

Civic Measurement Models: Measures competency for civic action, political efficacy and participatory citizen to assess young people's perceived ability to engage in civic action (e.g., organize a meeting), express their political voice (e.g., sign a petition), and critically analyze political messages.

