Additional protocol for identifying suicidality in survey participants: Because the intervention participant surveys assess for recent suicidal ideation, intent, plans, and attempts, we will implement protocols to immediately identify youth who report suicidal risk and connect them to the school counselor. The participant survey will be programmed in Qualtrics and the final screen for all youth will instruct them to: "Let the research team know you've finished the survey to receive your gift card. Code: complete." This will allow the team to verify survey completion and give the student their gift card. The Qualtrics survey will be programmed to include the youth's score on the suicide measures with the "Code: complete" message, such that students with no risk will get "Code: complete 1" and those with highest risk will get "Code: complete 5." This code is designed to not catch the attention of the student, but still allow the research staff to note the student's risk level, and then confidentially connect the student to the school counselor for further help outside of the intervention session.

References:

- 2. D'Augelli A, Grossman, Arnold H. Disclosure of sexual orientation, victimization, and mental health among lesbian, gay, and bisexual older adults. *Journal of interpersonal violence*. 2001;16(10):1008-1027.

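### Substance use goes to a repeated measures ANOVA with no stated items or recall window: lifetime items would hide quitting, and even past-30-day use is better analysed with adjustment for the September value

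*Protocol*

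**What the plan says.** The Data Analysis section of the protocol, repeated in the combined protocol and SAP, gives one method for the student cohort: "a cluster-randomized repeated measures ANOVA will be used to examine the intervention effects on minority stress, behavioral health outcomes, and coping skills". The Objectives section lists the "key behavioral health outcomes (depression, anxiety, PTSD, suicidality, substance use", so substance use falls under that ANOVA. The multilevel regression in the combined document concerns school-wide outcomes, not this cohort. Neither document gives a cohort model for binary, count or ordinal data.

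Under Instrumentation, the substance use entry reads "Measures individual's usage of various substances in their lifetime and within the past 30 days", and it also covers "the ways in which individuals have used marijuana, tobacco, or nicotine in the past 30 days". It gives no score, no recall window for the analysis and no choice of items. Cohort surveys are taken in September, November and May.

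**The concern.** The entry contains three kinds of item, and they behave differently under a test of change over time.

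- An accurately reported lifetime item can only stay the same or rise between September and May. A student who stops using leaves an ever-used answer unchanged. If the lifetime items are graded by number of occasions, which the documents do not say, stopping slows the rise but still cannot reverse it.
- Past-30-day use can move in both directions and reflects current behaviour.
- Ways of use are categories and have no mean to compare.

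Since the plan does not choose among them, the choice can be made after the data are seen, and some of the permitted choices would hide a real reduction in use. Separately, a repeated measures ANOVA treats September as one more outcome wave. Using it as a covariate is usually more efficient, and this matters with only 24 schools.

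**Working it through.** The plan states no power, rates or intraclass correlation (ICC), so there is no figure of its own to reproduce. What follows is an illustration.

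**From the documents:** 24 schools, 12 of them intervention schools; 12 students invited per school, so at most 12 × 12 = 144 per arm.

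**Assumed:** in September 50% have ever used and 30% used in the past 30 days; 15% of current users stop by May in control and 50% in intervention; 10% of never-users start in both arms. The test is a school-level t-test, two-sided 5%, with 22 degrees of freedom (critical value 2.074). School variation is placed in September prevalence, so it largely cancels from change and is left out below.

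**Expected May values**
- Past-30-day use, control: 0.30 × 0.85 + 0.50 × 0.10 = 0.305. Intervention: 0.30 × 0.50 + 0.05 = 0.200. Difference 0.105.
- Lifetime use, both arms: 0.50 + 0.05 = 0.55. Difference 0.

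**Power** ≈ Φ(difference/SE − 2.074), with SE = √[(V_control + V_intervention)/144].

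1. *Change in past-30-day use.* Control: −1 with probability 0.045, +1 with 0.05, V = 0.095 − 0.005² = 0.0950. Intervention: −1 with 0.15, +1 with 0.05, V = 0.20 − 0.10² = 0.1900. SE = √(0.2850/144) = 0.0445; 0.105/0.0445 = 2.36; power ≈ Φ(0.29) = 61%.
2. *Change in lifetime plus past-30-day use.* A starter now counts +2. Control V = 0.245 − 0.055² = 0.2420. Intervention V = 0.35 − 0.05² = 0.3475. SE = √(0.5895/144) = 0.0640; the difference is still 0.105, the ratio 1.64, and power ≈ Φ(−0.43) = 33%.
3. *Lifetime use alone.* Difference 0, so the rejection rate is the 5% level.
4. *May past-30-day use adjusted for September.* Variance of the September value: 0.30 × 0.70 = 0.21. Covariance with May: control 0.255 − 0.30 × 0.305 = 0.1635; intervention 0.15 − 0.30 × 0.20 = 0.0900. Slope = 0.2535/0.42 = 0.604. Residual variance: control 0.2120 − 0.1974 + 0.0765 = 0.0911; intervention 0.1600 − 0.1086 + 0.0765 = 0.1279. SE = √(0.2190/144) = 0.0390; ratio 2.69; power ≈ Φ(0.62) = 73%.

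Simulation of this case at ICC 0.02 gave 60%, 35% and 5% for items 1 to 3, which agrees.

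**Other assumed scenarios (simulated power)**

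| Scenario | Past-30-day | Lifetime | Combined |
|---|---|---|---|
| Quitting 10% v 50%, starting 8% in both arms, ever use 30–50%, current use 15–30%, ICC 0.03 | 34–78% | 4–5% | 16–49% (average) |
| Quitting 15% v 50% and starting 10% v 5% | 84% | 17% | 73% (sum) |
| Starting 10% v 5% only | 11% | 17% | 14% (sum) |

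**ANOVA against adjustment.** One simulation of the 24 × 12 layout, with benefit through quitting, gave 31% for repeated measures ANOVA on lifetime plus past-30-day use, 50% for that ANOVA on past-30-day use, 74% with September adjustment and 5% for a lifetime change test. The hand calculation above shows a smaller gain from adjustment, 61% to 73%. The direction is the same, and the size depends on how strongly September and May use are correlated.

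**The case against.** The best reply is that Instrumentation describes a questionnaire, not an outcome. Past-30-day items are collected, and no section says that lifetime or ways-of-use items enter the ANOVA or are added to the rest. That stands: the documents show an undefined outcome, not a wrong one. A reader might infer that the plan will average lifetime and nominal items, but the text does not support that.

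It is also true that the contrast between lifetime and past-30-day use is between items, not models, and that its zero for lifetime use follows from giving both arms the same initiation. When benefit comes only through fewer starters, lifetime use does slightly better (17% v 11%). That is why lifetime items are kept for initiation rather than discarded. The gain in the model comparison is from adjusting for September. A mixed logistic model was not itself simulated, and the calculation in item 4 is linear. The logistic or ordinal form is proposed because it fits the scale of the data.

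A stronger reading is tempting for suicidality: that the ANOVA will be run on a 1–5 risk code and so will miss benefit. The documents do not support it. The measure is "Six items assessing current suicidality that were adapted from the longer, treatment-based Columbia Suicide Severity Rating Scale". The code belongs to the protocol's procedure for identifying suicidality in survey participants ("The Qualtrics survey will be programmed to include the youth's score on the suicide measures"), where it lets staff connect a student to the counselor; it is not named as an efficacy outcome, and the procedure is absent from the combined document. Nor is an ordinal or binary replacement clearly better. Under a common odds ratio the mean code loses about 5 points of power (64% v 69% for a rank test). If severity falls but the share at any risk does not, assumed distributions gave 51% for the mean, about 15% for the rank test and 5% for any risk. Which scale has more power depends on the effect pattern.

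**Conclusion.** The point holds for substance use. The plan sends it to a repeated measures ANOVA without saying which items or recall window make up the outcome. If lifetime items are included, a benefit through reduced current use is diluted (61% to 33% in the worked case) or, with lifetime use alone, invisible (5%). For past-30-day use alone, leaving out September adjustment costs about 12 points in the worked case and 24 in the separate simulation (50% v 74%). That lifetime use cannot fall needs no assumption beyond accurate reporting. The sizes rest entirely on assumed prevalences, quitting and starting rates, ICCs and full attendance of 12 per school. Confidence is moderate. The point does not extend to how suicidality is scaled.

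**What to change.** In the Data Analysis sections of both documents:

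- Name past-30-day use as the substance use outcome, and list the substances in advance.
- Analyse it by a mixed logistic model (any use) or a mixed ordinal model (frequency), with a school random intercept, the September value as covariate and small-sample degrees of freedom for 24 schools. Report a risk difference.
- Use lifetime items only for initiation among students who were never-users in September.
- Report ways of use descriptively.

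The cost is SAP wording and some analysis code; no new data are needed. The downsides are one more model alongside the ANOVA, and rarely used substances may have to be collapsed before a model can be fitted. No change to the scale used for suicidality is proposed under this point.
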